2.1.2 Primary Endpoints

Endpoints	Summary Measure
Subjects experiencing treatment-emergent adverse events (TEAEs) including: 
 • SAEs • AESIs • CSL312-induced ADAs • Clinically significant abnormalities in laboratory assessments that are reported as AEs 	Number and proportion of subjects experiencing the specified safety events after treatment with investigational product (CSL312 or placebo)

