8.5.6 Follow-up Telephone Call

On Day 154 (\pm 5 days), the investigator (or delegate) will contact the subject by telephone to collect data on AEs (including acute exacerbation of IPF symptoms) and concomitant medications. The Follow-up Telephone Call should be scheduled to occur 90 days after the last administration of investigational product.

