9.4 Observation Period for Adverse Events

The observation period for the reporting of AEs and SAEs for an individual subject will start at the time at which written informed consent for participation in the current study is obtained and ends with the Follow-up Telephone Call.

If the investigator becomes aware of an SAE that started after the observation period has finished, and there is at least a possible causal relationship with the investigational product, the event must be reported to CSL (see [Section 9.6.3](#)).

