10.3.3 Safety Analyses

TEAEs will be coded using the Medical Dictionary for Regulatory Activities (MedDRA) version 24.1 (or higher). A TEAE is defined as an AE reported at or after the start of the first administration of study treatment. Only TEAEs will be summarized.

An overview summary of TEAEs, including counts and percentages of subjects with any of the following events, will be produced:

- TEAEs
- TEAEs related to study treatment
- TEAEs leading to permanent discontinuation of study treatment
- Serious TEAEs
- Serious TEAEs related to study treatment
- Fatal TEAEs

- Fatal TEAEs related to study treatment
- TEAEs by severity
- Treatment-emergent AESIs

TEAEs will be summarized by system organ class and preferred term. TEAEs will also be summarized by causality and severity. All TEAE summaries will be provided for each treatment group and overall.

The number and percentage of subjects with plasma anti-CSL312 antibodies will be summarized by treatment group and overall.

Laboratory evaluations (hematology, biochemistry, and urinalysis) will be summarized descriptively by treatment group.

Change from Baseline in DL_{CO} will be summarized using descriptive statistics by treatment group.

The Safety Analysis Set will be used for the safety analyses unless indicated otherwise.

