8.4 Study Periods Relative to Treatment

All data will be assigned to 1 of the 3 study time periods defined below.

- **Pre treatment** is defined as the time before the subject's first date / time of IP (Day 1).
- **On-treatment** (Treatment and Observation Period) is defined as the time from first date / time of IP up to Week 14 (Day 1 to Day 92).
- **Post treatment** begins after the end of the Treatment and Observation Period (Day 92) and continues through the Follow-up visit (follow-up telephone call) (Day 154).

9 Study Population

Unless otherwise stated, all tables and listings in this section will be based on the Safety Analysis Set.

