11.2 Adverse Events

AEs will be coded using the MedDRA dictionary (the MedDRA version will be populated in the tables output). AEs will start to be collected upon the subject's signing of the informed consent form (ICF). TEAEs, defined as AEs starting on or after the date (and time if available) of the first administration of IP (IV loading dose) through the end of the Treatment and Observation Period, will be summarized. The summary will be given by treatment group and overall. All AEs regardless of whether they were treatment-emergent or not will be listed.

Where AE start dates and/or times are missing or partially missing, AEs will be assumed to be treatment-emergent, except if the partial start dates and/or times or the AE end date and/or time indicate that the AE started before the first administration of IP (Table 2).

Table 2 TEAE Assignment in Case of Missing AE Start Date Elements

Missing elements of AE start	Rule	
Regardless of any missing information for AE start: AE end date / time < IP start date / time		non TEAE
Otherwise (ie, if AE end date / time \geq IP start date / time)		
- all		TEAE
- day and month	AE start year \geq IP start year	TEAE
	AE start year < IP start year	non TEAE
- day	AE start month / year \geq IP start month / year	TEAE
	AE start month / year < IP start month / year	non TEAE
- time	AE start date \geq IP start date	TEAE
	AE start date < IP start date	non TEAE

If AE start dates or end dates are missing or partially missing for an AE, no duration will be calculated. A missing category will be shown in summary tables by severity in case the severity is missing (the same is applicable for relationship to study treatment). No imputations for missing AE information will be done.

The AESIs defined for this study are:

- Bleeding events - Standardised MedDRA Query "Haemorrhages (SMQ)" (narrow)
- Thromboembolic events (TEE) - Standardized MedDRA Query "Embolic and thrombotic events (SMQ)" (narrow) consisting of:

- Embolic and thrombotic events, arterial (SMQ);
 - Embolic and thrombotic events, venous (SMQ);
 - Embolic and thrombotic events, vessel type unspecified and mixed arterial and venous (SMQ).
- Severe Hypersensitivity including anaphylaxis - Standardised MedDRA Query “Hypersensitivity (SMQ)” (broad), “Anaphylactic reaction (SMQ)” (broad), and “Anaphylactic/anaphylactoid shock conditions (SMQ)” (broad). Here, broad scope includes narrow and broad search.

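### SAP 11.2 closes the TEAE window at Day 92, so AEs collected up to the Day 154 call drop out of the by-arm primary safety counts, and SAP 5 does not say so

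*SAP*

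**What the plan says.** **Protocol.** Section 10.3.3 bounds the definition on one side only: "A TEAE is defined as an AE reported at or after the start of the first administration of study treatment. Only TEAEs will be summarized". Section 9.4 says that the AE and SAE observation period "ends with the Follow-up Telephone Call". Section 8.5.6 sets that call at Day 154 (±5), 90 days after the last dose, "to collect data on AEs (including acute exacerbation of IPF symptoms) and concomitant medications". The primary measure in Section 2.1.2 is the number and proportion of subjects with the specified safety events after treatment. It names no last day.

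**SAP.** Section 11.2 summarizes AEs starting on or after the date "of the first administration of IP (IV loading dose) through the end of the Treatment and Observation Period, will be summarized". Section 8.4 defines the on-treatment period as Day 1 to Day 92. The post-treatment period "begins after the end of the Treatment and Observation Period (Day 92) and continues through the Follow-up visit", which is Day 154. For everything else, Section 11.2 provides a listing: "All AEs regardless of whether they were treatment-emergent or not will be listed". The AE overview and frequency tables in 11.2 are all for TEAEs, serious or fatal TEAEs, or treatment-emergent AESIs.

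**Declared changes.** SAP 5 states that the planned analyses are unchanged and names only the modified Screened Analysis Set.

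**The concern.** AEs, SAEs and AESIs are components of the primary endpoint, and the endpoint is a number and a proportion per arm. A by-subject listing does not supply that. The follow-up call exists to collect AEs, including acute exacerbations of IPF, yet an event learned from it with a complete start date and time after Day 92 enters no by-arm table. If the SAP is followed as written, both arms report incidence over a shorter period than the protocol's definition covers, and someone checking SAP 5 for departures would not learn of it.

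The SAP also treats late follow-up unevenly. The disposition table in Section 9.1 still counts withdrawals up to the Follow-up Visit by arm. The IDMC tables in Section 4.5.1 refer back to Section 11 and set no window of their own.

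The reach is limited in two ways. Scheduled ADA and laboratory sampling ends at Day 92, so those components do not change. SAP 4.1.1 states that there is no primary hypothesis, so no test or error rate is involved.

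**Working it through.** **Inputs from the documents.** First dose Day 1; last dose Day 64; EOT Visit Day 92 (±2); call Day 154 (±5); 70 evaluable subjects, 35 per arm; 12% dropout; half-life about 18 days after SC dosing, Tmax about 7 days, SC bioavailability about 50%.

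**The plan's own dates.** 64 + 90 = 154, and Week 14 begins on Day 13 × 7 + 1 = 92. Both agree with the schedule.

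**Uncounted calendar time**
- Nominal: 154 − 92 = 62 days, out of 154 − 1 = 153 days after first dose; 62/153 = 40.5%. (Counting Day 1 as a full day gives 62/154 = 40.3%.)
- Visit windows: (149 − 94)/(149 − 1) = 55/148 = 37.2%, up to (159 − 90)/(159 − 1) = 69/158 = 43.7%.
- After the last dose: 92 − 64 = 28 days are counted and 62 of the 90 are not. Day 92 is 28/18 = 1.56 half-lives after the last dose; simple decay, ignoring SC absorption, leaves 0.5^1.56 = 34%.

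**Uncounted subject-time**
- 70 × 62 = 4,340 subject-days; 35 × 62 = 2,170 per arm, and 2,170/365.25 = 5.9 subject-years.
- Share of all subject-days with 12% dropout by Week 14 and none later. Spread evenly over Days 1-92: 0.88×62 / (0.88×62 + 0.88×91 + 0.12×45.5) = 54.56/140.10 = 38.9%. All leaving at Day 92: 54.56/(54.56 + 91) = 37.5%. All leaving at Day 1: 40.5%.

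**Effect on a reported percentage (illustration; the incidences are assumed)**

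Constant hazard, full follow-up: tabulated = 1 − (1 − p)^(91/153), where p is the incidence to Day 154. The range uses exponents 93/148 and 89/158.
- p = 10%: 6.1% (5.8% to 6.4%).
- p = 20%: 12.4% (11.8% to 13.1%).

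Constant hazard, 12% dropout spread evenly over Days 1-92, crude proportion of dosed subjects. With λ = −ln(1 − p)/153 and D = 1 − (1 − e^(−91λ))/(91λ), the proportion to Day 154 is 0.88p + 0.12D, and to Day 92 it is 0.88(1 − e^(−91λ)) + 0.12D.
- p = 10%: 9.2% becomes 5.7%.
- p = 20%: 18.4% becomes 11.7%.

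CSL312 arm only, hazard proportional to concentration, full follow-up. This is a one-compartment sketch: half-life 18 d, ka = 0.356/day to give Tmax 7 d, 300 mg IV on Day 1, 600 mg SC on Days 8, 36 and 64, F = 0.5 (0.40 to 0.66 assumed as a range). The share of exposure after Day 92 is 0.135 (0.128 to 0.142).
- p = 10%: 1 − 0.9^0.865 = 8.7% (8.6% to 8.8%).
- p = 20%: 1 − 0.8^0.865 = 17.6% (17.4% to 17.7%).

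**Missing start elements.** Table 2 in SAP 11.2 and its lead-in test only the first-dose boundary. Read literally, an AE dated Day 120 without a clock time is a TEAE, because its date is after the IP start date; the same AE with a time is not. A count could then turn on whether a time was recorded.

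**The case against.** - **The protocol itself is not uniform about Day 92.** Section 8.5.5 says scheduled participation ends at the EOT Visit with no further procedures, and 9.6.3 treats that visit as a boundary for entering related SAEs. This is so, and the passages need reconciling. But 8.5.5 defines no TEAE window, and the very next section schedules the Day 154 AE call.
- **The SAP may only be elaborating.** Protocol 10.3.1 leaves the full description of analyses to the SAP, and 10.3.3 is silent on an end. The SAP was also written against Amendment 2, which is not available; the Amendment 3 change list names no TEAE change but includes unspecified minor clarifications. Some uncertainty about the earlier text remains. Against the protocol in hand, an added end date that removes collected events from the primary counts is a change, and SAP 5 took the trouble to declare a smaller one.
- **Calendar time is not events.** This stands. Late AEs come from a single call, so a constant reporting rate is doubtful, and exposure weighting makes the loss much smaller. Late AEs admitted through Table 2 would reduce it further.
- **A Day 92 table can be legitimate.** Agreed, if it is declared and accompanied by by-arm counts to the call.
- **The IDMC charter has not been seen.** True, so the practical limits on IDMC output are unknown.
- **The analysis is descriptive and uses the same cut-off in both arms.** True, but description is the whole of this primary endpoint.

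**Conclusion.** The concern holds. SAP 11.2 with 8.4 narrows the protocol's TEAE definition without declaring it, and the narrowing changes the by-arm primary AE, SAE and AESI counts. About 40% of nominal post-first-dose AE collection time (37% to 44% across the visit windows) falls outside the tables.

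How many events that represents cannot be worked out from the documents. The illustrations bracket the effect on an assumed 10% incidence between 6.1% (constant hazard) and 8.7% (hazard following concentration, CSL312 arm only), both with full follow-up. The finding itself rests on the text, not on these assumptions. It should be corrected before database lock.

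**What to change.** 1. **SAP 11.2:** define TEAEs as AEs starting on or after first IP through the Follow-up Telephone Call, or last contact if the call is not made. Use this for the primary AE, SAE and AESI tables, with an optional split at Day 92 by the periods in SAP 8.4.
2. **Table 2 and its lead-in:** add the same upper bound, so that an AE with missing start elements is a TEAE unless the known elements place it before first IP or after the call.
3. **SAP 5:** state the chosen upper bound, since protocol 10.3.3 has none, and give the reason for any Day 92 table that is kept.
4. **Protocol, a separate point on which complete SAE counts depend:** Section 9.6.3 says that related SAEs after the EOT Visit are not entered into the eCRF. Section 9.4, and the 9.6.3 rule that all SAEs during the study are entered, point the other way. Reconcile these, together with 8.5.5, so that SAEs up to the call reach the clinical database. Otherwise the wider tables could gain unrelated late SAEs and miss related ones, and some related late SAEs might not reach even the listings.

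The cost is SAP wording, minor programming and one protocol clarification, with no new visits or assessments. Reported AE, SAE and AESI percentages can stay the same or rise, so they may look somewhat less favourable.

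### The SAP ends treatment-emergent AEs at Day 92 while the protocol sets no end date and collects AEs to Day 154, so later SAEs, AESIs and fatal events are left out of, or inconsistently admitted to, the by-arm safety tables

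*SAP*

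**What the plan says.** **Protocol.** Section 10.3.3 states: "A TEAE is defined as an AE reported at or after the start of the first administration of study treatment". It gives no end date and adds: "Only TEAEs will be summarized". Under 9.4 the observation period for AEs and SAEs "ends with the Follow-up Telephone Call". Under 8.5.6 that call, on Day 154 (±5), is made "to collect data on AEs (including acute exacerbation of IPF symptoms) and concomitant medications". The primary summary measure in 2.1.2 is the number and proportion of subjects with the specified events after treatment, with no cut-off day.

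**SAP.** Section 11.2 confines the summaries to AEs with onset from the date "of the first administration of IP (IV loading dose) through the end of the Treatment and Observation Period, will be summarized". In 8.4 the on-treatment period "is defined as the time from first date / time of IP up to Week 14 (Day 1 to Day 92", and the post-treatment period "begins after the end of the Treatment and Observation Period (Day 92) and continues through the Follow-up visit", at Day 154. For missing or partial start dates, 11.2 says that "AEs will be assumed to be treatment-emergent, except if the partial start dates and/or times or the AE end date and/or time indicate that" the event began before first dosing, and Table 2 puts this into rules. SAP 5 reports no change to the planned analyses and mentions only the Screened Analysis Set.

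The general AE tables in SAP 11.2 (overview, AESIs, serious events, fatal events, system organ class and preferred term) are all TEAE tables. None uses the post-treatment period of SAP 8.4. All AEs, SAEs and AESIs are listed by subject.

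**The concern.** Safety is the primary objective, and SAEs and AESIs are named parts of the primary endpoint. A reader of the protocol expects by-arm counts over the whole AE collection period. A reader of the SAP gets counts that formally stop 62 days earlier.

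Day 92 ends a dosing interval, not the drug's effect. It is 28 days after the last SC dose. Protocol 3.3.2 projects a median kallikrein inhibition of at least 90% at the low point of that interval, using a model from healthy volunteers and HAE patients. Protocol 1.4.2 names bleeding and thromboembolism as potential risks of blocking FXIIa. The protocol itself uses 90 days after the last dose for contraception (7.4) and pregnancy reporting (9.6.6).

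What is at stake is whether late bleeding, thromboembolic, serious and fatal events appear in the randomized comparison. As written, their inclusion can also turn on how completely a start date was recorded.

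**Working it through.** **1. The plan's own timing.** The last dose is on Day 64 (protocol 8.5.3). Day 64 + 90 = Day 154, which reproduces the planned day of the call. Day 64 + 28 = Day 92, the end of the last SC interval.

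**2. Size of the window.**
- Share of the time after first dose: (154 − 92)/154 = 62/154 = 0.403.
- With the call at Day 149: 57/149 = 0.383. At Day 159: 67/159 = 0.421.
- Moving the Day 92 visit by its ±2 days as well: 55/149 = 0.369 to 69/159 = 0.434.
- Share of the 90 days after the last dose: 62/90 = 0.689.

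**3. Drug still present.** The half-life after SC injection is about 18 days (protocol 3.3.2). At Day 92, 28/18 = 1.56 half-lives have passed and 0.5^1.56 = 0.34 remains. At Day 154, 90/18 = 5.0 half-lives have passed and 0.5^5 = 0.03 remains. This is simple decay from the last dose and ignores absorption and accumulation.

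**4. The two SAP rules applied to one event.** Take an AE starting on Day 120 that ends after first dosing.

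| Start recorded | Rule that applies | Result |
|---|---|---|
| Date and clock time | Definition in 11.2, end at Day 92 | Not a TEAE |
| Date, no clock time | Table 2, time missing: start date on or after first dose | TEAE |
| Month and year only | Table 2, day missing: start month on or after first-dose month | TEAE |
| Nothing | Table 2, all missing | TEAE |

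The second row matters most, because 11.2 uses the clock time only where one is available. One programmer could apply Table 2 literally. Another could use it only to settle the lower limit and then impose Day 92. Both could claim to follow the SAP, and their primary counts would differ. The documents do not say how often AE clock times are recorded.

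**5. Illustration of counts (not a forecast).** Assume a constant hazard, no dropout, 40 subjects per arm and a risk p of a first event by Day 154. The risk by Day 92 is q = 1 − (1 − p)^(92/154).

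| p (assumed) | q | Subjects by Day 154 | By Day 92 | Left out by a strict Day 92 cut |
|---|---|---|---|---|
| 0.05 | 0.0302 | 2.0 | 1.21 | 0.79 |
| 0.10 | 0.0610 | 4.0 | 2.44 | 1.56 |
| 0.20 | 0.1248 | 8.0 | 4.99 | 3.01 |
| 0.30 | 0.1919 | 12.0 | 7.68 | 4.32 |

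That is 36% to 40% of affected subjects.

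For deaths, suppose the median survival of 3 to 4 years after diagnosis (protocol 1.1) acted as a constant hazard from Day 1, with S(d) = 0.5^(d/(m × 365.25)). Then 80 × [S(92) − S(154)] = 2.90 for m = 3 and 2.22 for m = 4. The true hazard in an already diagnosed cohort could be higher or lower. A late death from an AE that began by Day 92 is still counted as a fatal TEAE.

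**6. Related SAEs.** Protocol 9.6.3 sends related SAEs after the End-of-Treatment Visit to the sponsor and keeps them out of the eCRF, although 9.4 keeps the observation period open until the call. Widening the SAP window alone would not bring those events into eCRF-based tables, and they could be missing from the listings too.

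**The case against.** The case for leaving the plan alone has real content.

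- **Day 92 has some footing in the protocol.** Section 8.5.5 puts the scheduled end of participation at the Day 92 visit, and 9.6.3 treats that visit as a boundary. This shows that the protocol is not uniform. It does not supply an end date for the TEAE in 10.3.3 or override 9.4.
- **There is a design reason to separate the periods.** Antifibrotics (except for disease progression) and anticoagulants other than LMWH are barred only through Day 92 (protocol 7.3). One pooled Day 1 to 154 count would mix in bleeding on newly started anticoagulants. This stands, and it shapes the fix.
- **The 40% is calendar time.** Days 93 to 154 are covered by one telephone call, against 11 visits before. Hypersensitivity should cluster around the four doses, all given by Day 64. Both points weaken the constant-hazard illustration.
- **Late events are not lost.** The trial is descriptive, with no hypothesis and about 80 subjects. Late events in the eCRF could be counted by hand from the listings, and deaths may show in the by-arm disposition reasons (SAP 9.1). Scheduled ADA and laboratory samples end at Day 92 and are unaffected. Even so, listings are not the number and proportion by arm that the primary endpoint promises.
- **The SAP predates the current protocol.** It was written against Amendments 1 and 2, and the current protocol is Amendment 3. The Amendment 3 log names no TEAE change, but the Amendment 2 wording is not available. It therefore cannot be shown that SAP 5 was wrong when signed, only that the difference from the current protocol is undeclared.

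A reader might infer that every late event certainly drops out of the by-arm tables. Table 2 does not support that, because it admits a late AE without a clock time. A reader might also take the general fatal-TEAE line as the only count of deaths. SAP 7.1 and 11.2 add COVID-19 fatal lines, though these too are limited to TEAEs.

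**Conclusion.** The inconsistency is real and should be corrected before database lock. SAP 11.2 with 8.4 ends TEAEs at Day 92, the protocol sets no end date, and Table 2 contradicts the SAP's own definition. Events starting on Days 93 to 154 are therefore excluded from, or inconsistently included in, the by-arm tables for the primary endpoint.

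The firm figures are 62 of 154 days after first dose (40%, or 37% to 43% across visit windows), 62 of 90 days after the last dose (69%), and a boundary 1.6 half-lives after the last dose. The last figure rests on the protocol's half-life of about 18 days. The event and death counts are illustrations under stated assumptions, not bounds. Nothing in the documents suggests that the cut favours either arm, and no imbalance is claimed.

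**What to change.** 1. **SAP 11.2.** Define a TEAE as an AE with onset from first dosing through the Follow-up Telephone Call (Day 154 ±5). Present SAEs, AESIs and fatal events by arm separately for Days 1 to 92 and Days 93 to 154, because restricted antifibrotics and anticoagulants may start after Day 92.
2. **Alternative.** Keep Day 92, declare it in SAP 5 as a change from the protocol, and add one by-arm post-treatment table of SAEs, AESIs and deaths, using the period already defined in SAP 8.4.
3. **SAP Table 2.** Give it the same end date as the chosen definition, so that classification does not depend on whether a day or clock time was recorded.
4. **Protocol 9.6.3.** Move the point after which related SAEs stay out of the eCRF from the End-of-Treatment Visit to the Follow-up Telephone Call. If the protocol is not amended, reconcile the tables and listings with SAEs reported to the sponsor outside the eCRF.

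A count of deaths found only through public records (protocol 4.3.3) is optional.

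The cost is SAP wording, a few extra table columns or one extra table, and one phrase in the protocol or a reconciliation step. No visit or assessment is added, because AEs are already collected to Day 154.

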9.3 Causality of Adverse Events

The causal relationship of an AE to the investigational product **must always be assessed** by the investigator. All AEs will be classified as either **related** or **not related** to the investigational product. If a causality assessment is not provided for an AE (including an SAE), that AE will be considered related to the investigational product.

The degree of certainty with which an AE is attributed to investigational product or an alternative cause (eg, natural history of the underlying disease, concomitant therapy) will be determined by how well the event can be understood in terms of:

- Known pharmacology of investigational product.
- Clinically and / or pathophysiologically plausible context.
- Reaction of a similar nature previously observed with similar products, or reported in the literature for similar products as being product related (eg, headache, facial flushing, pallor).

- Plausibility supported by the temporal relationship (eg, the event being related by time to administration or termination of treatment with investigational product, drug withdrawal, or reproducible on rechallenge).

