4.5.1 Independent Data Monitoring Committee

The roles and responsibilities of the independent data monitoring committee (IDMC) and the safety data review schedules are described in the IDMC charter. Operationally, since the IDMC is ad-hoc and can be triggered before SAS programming can be done to generate summary output, in this case, only data dump listings will be generated. Otherwise, those summary tables will be provided for the following (along with their supporting listings):

- Demographics;
- Treatment and exposure;
- AE overall summary, SAEs, AEs, AESIs.

Other safety analysis output as listed below, will be provided as data listings:

- Vital signs, physical exams and respiratory tests;
- Safety laboratory parameters / urinalysis;
- ECG;
- Medical history;
- Concomitant medication;
- Spirometry.

Please refer to [Sections 9, 10, and 11](#) of this SAP for descriptions of the analysis listed above.

5 Changes from the Protocol Planned Analyses

There are no changes to the planned analyses as previously documented in the CSP.

The definition of screened analysis set was slightly modified, please refer to Section 6.1.

6 Study Analysis Sets

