An overview summary of TEAEs, including number and percentages of subjects as well as the number of events will be provided including the following:

- Any TEAE;
- TEAEs related to study treatment;
- TEAEs in each severity category;
- TEAEs leading to discontinuation of study treatment (obtained from AE eCRF);
- TEAEs leading to study withdrawal (obtained from “End of Treatment” or “Conclusion of Subject Participation” eCRF);
- TEAEs leading to dose adjustments or dose interruptions;
- Treatment-emergent AESIs;
- Treatment-emergent AESIs related to study treatment;
- Serious TEAEs;
- Serious TEAEs related to study treatment;
- Fatal TEAEs.

COVID-19 associated TEAEs will be included in AE overview table as (as described in [Section 7.1](#)):

- Any TEAE (related/not related);
- Serious TEAE (related/not related);
- Fatal TEAE (related/not related);

- TEAE leading to discontinuation of study treatment (obtained from AE eCRF) (related/not related);
- TEAE leading to dose adjustments or dose interruptions (related/not related);
- TEAE leading to study withdrawal (related/not related);
- TEAE by maximum severity (mild, moderate, severe, missing).

The following frequency tables will be generated for TEAEs, including number and percentages of subjects and the number of events:

- TEAEs by SOC and preferred term;
- TEAEs by preferred term;
- TEAEs by SOC, preferred term, and maximum severity (without number of events);
- Related TEAEs by SOC and preferred term;
- Related TEAEs by preferred term;
- Treatment-emergent AESIs by preferred term;
- Serious TEAEs by SOC and preferred term;
- Related serious TEAEs by SOC and preferred term;
- TEAEs with result in drug discontinuation;
- TEAEs related to COVID-19 infection.

AEs will be presented in summaries by decreasing overall frequency (overall frequency as the number of subjects with that AE beginning with the SOC, followed by preferred term). If 2 AEs have the same overall frequency, the AEs will be ordered alphabetically.

The following by-subject listings will be provided:

- All AEs;
- SAEs;
- AEs leading to study withdrawal or permanent discontinuation of study treatment;
- AESIs by type of AESI;
- Subjects receiving COVID-19 vaccine;
- AEs occurring within 7 days after COVID-19 vaccine administration.

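### SAP 11.2 leaves adverse events with no causality assessment as missing where Protocol 9.3 counts them as related, and the SAP overview drops the related-fatal row; neither departure is declared

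*SAP*

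**What the plan says.** Protocol 9.3 makes causality binary: "All AEs will be classified as either related or not related to the investigational product". It then gives a default for blanks: "If a causality assessment is not provided for an AE (including an SAE), that AE will be considered related to the investigational product".

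SAP 11.2 handles blanks differently. It provides a missing category in the severity tables, adds that "the same is applicable for relationship to study treatment", and closes with "No imputations for missing AE information will be done".

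The same SAP section plans several outputs that depend on relatedness. The overview has rows for related TEAEs, for "Serious TEAEs related to study treatment" and for related AESIs. The frequency tables include "Related TEAEs by SOC and preferred term", related TEAEs by preferred term, and related serious TEAEs.

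SAP Section 5 says "There are no changes to the planned analyses as previously documented in the CSP" and then notes one modification, to the Screened Analysis Set.

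Protocol 10.3.3 also lists "Fatal TEAEs related to study treatment" among the overview rows. The SAP 11.2 overview has a row for fatal TEAEs but none for related ones. Only the COVID-19 subset is split by relatedness for fatal events.

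**The concern.** The two documents give different answers for the same blank field. Under the protocol the event is related. Under the SAP it is missing and stays missing, so the natural reading is that it does not enter any row or table restricted to related events. A programmer working from the SAP alone would then produce related counts that do not follow the protocol's definition, and nothing in SAP Section 5 would alert the reader of the study report.

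Safety is the primary objective, and the protocol itself plans summaries of related TEAEs and related serious TEAEs. The protocol's default is conservative. The SAP takes a similarly cautious line elsewhere in the same section: an event with a missing start date is assumed treatment-emergent unless the available dates show otherwise.

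The missing fatal row is a second, smaller departure that does not depend on blank data.

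**Working it through.** **Text comparison**

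| Item | Protocol | SAP |
|---|---|---|
| Causality levels | Related / not related (9.3) | Related / not related / missing (11.2) |
| Blank causality | Counts as related (9.3) | Own category, no imputation (11.2) |
| Related fatal TEAEs | Overview row planned (10.3.3) | Not in overview, except for the COVID-19 subset (11.2) |
| Declared as a change | – | No (Section 5) |

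The SAP was written against protocol Amendment 2, and the current protocol is Amendment 3. None of the specific changes itemised for Amendment 3 concerns causality or the adverse event overview, so the log does not explain the mismatch.

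The SAP's rule is also incomplete. None of the TEAE frequency tables listed in 11.2 breaks events down by relationship level; they are restricted to related events. The COVID-19 rows in 7.1 and 11.2 offer related / not related only, although their severity row does list missing. A blank relationship has no cell there.

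**Denominator.** The documents state no related-event figure to reproduce. The planned sample size can be checked: 70 / (1 − 0.12) = 79.5, rounded up to 80, or 40 per arm, as in Protocol 10.1 and SAP 4.4. The Safety Analysis Set contains everyone treated, so n = 40 is the natural denominator; 35 is shown as a lower case.

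**Effect within an arm.** Let m be the number of subjects in an arm who have a blank-causality event and no other related event in the row concerned. The SAP count falls below the protocol count by m subjects, or m/n. The documents do not give m, so 0 to 4 is an assumed range for illustration.

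| m | n = 40 | n = 35 |
|---|---|---|
| 0 | 0 | 0 |
| 1 | 2.5 points | 2.9 points |
| 2 | 5.0 | 5.7 |
| 3 | 7.5 | 8.6 |
| 4 | 10.0 | 11.4 |

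Event counts, where shown, fall by one for each blank event, whether or not the subject has another related event.

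**Effect on the difference between arms.** With n = 40 in each arm, using the SAP rule instead of the protocol rule changes the CSL312-minus-placebo difference by −(m for CSL312 − m for placebo)/40. One affected subject on CSL312 only gives −2.5 points; one on placebo only gives +2.5; one in each arm gives 0.

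**The case against.** The strongest reply is that blanks should be rare. Protocol 9.3 requires the investigator always to assess causality, 9.6.3 requires it to be entered for every SAE, and 13.5.2 has electronic checks and queries. For SAEs at database lock the number may well be zero. This stands, and it makes the understatement conditional. It does not remove the conflict, because both documents provide for blanks and provide differently. The minimum SAE reporting items in 9.6.3 do not include causality. The IDMC summary tables (SAP 4.5.1) include the overall adverse event summary on ongoing data, where more fields may be unresolved; that last step is an inference.

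It can also be said that nothing is hidden, since all adverse events are listed and a missing category is promised, and that the SAP never says outright that blanks are left out of related rows. Both points are fair. Exclusion is the natural reading of no imputation, and the listings do not correct the tables.

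Four stronger readings are tempting, and the documents do not support them:

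- *The rule always favours the product.* It lowers the absolute related count in whichever arm has blanks. A blank on placebo makes CSL312 look worse by comparison, and nothing in the plan suggests that blanks would concentrate in one arm.
- *It weakens the halting rules.* Protocol 3.9.2 acts on a judgement by the investigator or the sponsor about an individual case, or on an overall pattern of events, not on counts from an SAP table.
- *It changes the primary endpoint.* Its components (Protocol 2.1.2, SAP 4.1) carry no relatedness condition.
- *One subject could change the related count by half.* The COVID-19 study described in Protocol 1.2.3.4 had 2/58 and 2/59 subjects with related TEAEs (3.4% each), and one more would make 3/58 = 5.2%. But that study gave a single IV dose. This trial adds three SC doses, and injection site reactions were more common with SC CSL312 than with SC placebo in the phase 1 study (1.2.3.1). Related events may be more numerous here, so the relative effect could be much smaller.

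On the fatal row, an event that results in death is serious by definition (Protocol 9.1.2), so a related one still enters the related serious TEAE row and table. What is lost is the ability to read the related fatal count directly from the overview.

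**Conclusion.** The contradiction is real and undeclared. Whenever causality is blank at analysis, the SAP gives related-TEAE, related serious TEAE and related AESI counts in that arm that are lower than the protocol's rule would give: 2.5 percentage points for each affected subject at 40 per arm, and zero if nothing is blank. This assumes that a missing relationship is excluded from rows restricted to related events, that about 40 subjects per arm are treated, and that the affected subject has no other related event in that row. The number of blanks is unknown and may be small.

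The omitted related-fatal row is a separate undeclared departure from Protocol 10.3.3 with limited loss of information. Both are worth correcting, as reporting rules that differ from the protocol rather than as threats to the trial's safety monitoring.

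**What to change.** In SAP 11.2:

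- State that adverse events with missing relationship are counted as related, following Protocol 9.3, in all related-event summaries: TEAEs, serious TEAEs, AESIs and the COVID-19 related / not related rows, including those described in SAP 7.1. Show the blank as entered in the by-subject listings.
- Keep the missing category for severity only, and exempt relationship from the no-imputation sentence.
- Restore the related-fatal row in the overview table.

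If the sponsor prefers to keep a missing relationship category, declaring and justifying it in SAP Section 5, with an additional count under the Protocol 9.3 rule, would also resolve the causality conflict.

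The cost is about two sentences, one derived flag and one table row. The downside is that related counts may be slightly less favourable.
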